6.3. Stopping and Discontinuation Criteria

- 6.3.1. Discontinuation Criteria related to the Study
 - Insufficient recruitment
 - Continuous serious protocol violation and deviation

6.3.2. Discontinuation Criteria related to the Patient

Patients will be advised in the Informed Consent Forms that they have the right to withdraw from the study at any time without prejudice, and may be withdrawn at the Investigator's / Sponsor's discretion at any time. In the event that a patient drops out of the study or is withdrawn, the withdrawal / study termination page in the CRF should be completed. On the withdrawal page the Investigator should record the date of the withdrawal, the person who initiated withdrawal and the reason for withdrawal. Reasonable effort should be made to contact any patient lost to follow up during the course of the study in order to complete assessments and retrieve any outstanding data and study supplies.

Withdrawn by the Investigator due to

- Serious Adverse Drug Reaction
- Lack of efficacy

- Consent withdrawn
- Administrative reasons

The patient or his/her representative requested withdrawal due to

- An Adverse Event for which the Investigator did not consider removal from the study.
- Perceived insufficient therapeutic effect.
- Withdrawal of consent for any other reason (data recorded until withdrawal will be kept in the database if not explicitly denied by the patient).

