13.12.2. Handling of Missing Data

In order to identify each type of missing data, outcome scales will be coded for every patient and visit according to the following scheme (see also Bagiella, 2010):

1 = valid (complete task)

2 = unable to complete (TBI-related neurological reason) [describe reason]

3 = not completed (different reasons, not TBI related) [describe reason]

Date: 040418

STUDY ID: CAPTAIN - rTMS

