13.12.4. LPCF Imputation

For outcome scales with code "3" a LPCF replacement will be introduced (Last Percentile Carried Forward) as far as previous follow-up evaluations exist. This method carries forward the actual status information of the patient population, using the percentile value with back transformation to raw scale, instead of last value carried forward. This approach was recently developed and recommended by O'Brien, Zhang and Bailey (2005) for the analysis of data from chronic, progressive diseases as dementia. According to their simulation study the calculated estimators should be negligibly biased by missing data. If no general change of patients over time occurs the method is more or less identical with LOCF (Last Value Carried Forward), if change occurs bias is minimized.

If no previous follow-up measurement exists, the outcome scale remains missing. It is important to note that the chosen multivariate test procedure (Wei-Lachin procedure) can handle partially missing single scales of type MCAR (missing completely at random).

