13.13.3. ITT Population (Full Analysis Set)

ITT population is defined as all patients who have no "severe" violation of entry criteria, had at least one dose of medication and at least one post-baseline observation of at least one primary efficacy criterion ("modified" ITT). This way ITT is defined in the sense of the "full analysis set" according to ICH E9 § 5.2. ("Analysis Sets") . ITT population will be used for all efficacy analyses.

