13. STATISTICAL ANALYSES

13.1. Study Patients

Patients will be advised in the Informed Consent Forms that they have the right to withdraw from the study at any time without prejudice, and may be withdrawn at the Investigator's / Sponsor's discretion at any time. In the event that a patient drops out of the study or is withdrawn, the withdrawal / study termination page in the CRF should be completed. On the withdrawal page the Investigator should record the date of the withdrawal, the person who initiated withdrawal and the reason for withdrawal. Reasonable effort should be made to contact any patient lost to follow up during the course of the study in order to complete assessments and retrieve any outstanding data and study supplies.

Withdrawn by the Investigator due to

- Serious Adverse Drug Reaction
- Lack of efficacy
- Consent withdrawn
- Administrative reasons

The patient or his/her representative requested withdrawal due to

Cerebrolysin and repetitive Transcranial Magnetic Stimulation (rTMS) in patients with Traumatic Brain Injury

- An Adverse Event for which the Investigator did not consider removal from the study.
- Perceived insufficient therapeutic effect.
- Withdrawal of consent for any other reason (data recorded until withdrawal will be kept in the database if not explicitly denied by the patient).

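### The Investigator may withdraw a patient from the study for lack of efficacy, and nothing then requires the two outcome visits

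*Protocol*

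**What the plan says.** Protocol 6.3.2 states that patients "may be withdrawn at the Investigator's / Sponsor's discretion at any time". Its list of Investigator reasons includes "Lack of efficacy", with no threshold and no timing. The patient-side counterpart is "Perceived insufficient therapeutic effect". SAP 13.1 repeats this text, including the instruction that begins "In the event that a patient drops out of the study or is withdrawn, the withdrawal / study termination page", so a single CRF page serves for both withdrawal and study termination.

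The only instruction to retrieve data reads "Reasonable effort should be made to contact any patient lost to follow up during the course of the study in order to complete assessments". It names patients lost to follow-up and does not mention patients whom the Investigator withdraws.

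Other parts of the plan bear on what happens next:

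- **Schedule (protocol 11.1).** The last treatment cycle ends on day 100. The first efficacy evaluation after baseline is on day 101 and the second on day 180.
- **Missing-data codes (protocol 13.12.2 to 13.12.4).** Worst-rank imputation is kept for patients who cannot do a test for a TBI-related neurological reason. The other code, "3 = not completed (different reasons, not TBI related"), leads to LPCF (last percentile carried forward). Where there is nothing to carry forward, "If no previous follow-up measurement exists, the outcome scale remains missing".
- **Modified ITT (protocol 13.13.3, SAP 10).** Entry needs one dose and "at least one post-baseline observation of at least one primary efficacy criterion".
- **Compliance (protocol 11.2 and 13.15, SAP 13.3).** Each infusion and rTMS session is dated. Compliance under 80% excludes a patient from the per-protocol set only.

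**The concern.** A patient withdrawn by the Investigator is not lost: the site knows where the patient is and the scores could be obtained. As written, though, the withdrawal is from the study, and no sentence keeps the patient in Visits 1 and 2. The compliance and ITT rules let an under-treated patient be analysed if a score exists, but they do not secure that score after withdrawal.

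A patient withdrawn because treatment seems not to work is missing for a reason tied to outcome. Protocol 13.12.1 itself warns that ignoring such data may introduce bias, and 13.12.4 claims only that the Wei-Lachin test copes with partly missing scales that are missing completely at random. Both visits enter the primary analysis, so a withdrawal before Visit 1 removes the patient's whole contribution.

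**Working it through.** **1. Tracing the rule**

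- *Withdrawal before day 101.* There is no follow-up score and hence no LPCF value. The scale stays missing (13.12.4) and the patient fails the post-baseline condition for the modified ITT set (13.13.3).
- *Withdrawal after day 101.* Code 3 fits best (a reading, since the plan does not name this case). The Visit 1 percentile is carried forward and the patient stays in the set.

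**2. The plan's own figure**

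Inputs from protocol 13.9: one-sided alpha 0.05, power 80%, MW 0.64, correlation 0.4, 10% allowance. With the Noether formula and k equally correlated scales:

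n = (1.645 + 0.842)² / (6 × 0.14²) × (1 + (k − 1) × 0.4) / k

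For k = 9 this is 52.6 × 4.2/9 = 24.5, rounded up to 25. Then 25 × 1.1 = 27.5, so 28 per group against the stated 30. The plan does not state k or the between-visit correlation, so an exact match cannot be expected. The sample size is not in question here.

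**3. Size of the shift if patients are lost before Visit 1**

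Set-up: 30 versus 30 patients, 9 scales at 2 visits, normal scores, d = 0.5 and between-scale correlation 0.4 (both from 13.9). Assumed: same-scale correlation between visits of 0.4 or 0.8. The estimate is the unweighted mean of the 18 Mann-Whitney values, each P(test better) + 0.5 P(tie). With full data it is 0.637 to 0.638. There were 2,000 runs per setting.

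The withdrawn patients are the lowest of all 60 on a selection score that correlates to a chosen degree with the mean Visit 1 score, so one cutoff applies to both arms. Shift in average MW with 6 of 60 (10%) lost:

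| Selection correlation | Between-visit 0.4 | Between-visit 0.8 |
|---|---|---|
| 0 | 0.0000 | +0.0002 |
| 0.32 | -0.0022 | -0.0026 |
| 0.5 | -0.0050 | -0.0061 |
| 0.71 | -0.0102 | -0.0127 |
| 1 | -0.0200 | -0.0251 |

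The standard error is at most 0.0005. Against the design effect of 0.64 − 0.50 = 0.14, the range from 0.32 to 1 is 0.0022/0.14 = 1.6% to 0.0251/0.14 = 18%. Over the same correlations, 3 of 60 lost gives -0.0013 to -0.0152, and 2 of 60 gives -0.0009 to -0.0111.

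The negative sign comes from the split between arms. If the treatment works, a common cutoff takes more patients from CRB alone: 3.6 against 2.4 at correlation 0.32, and 4.7 against 1.3 at correlation 1.

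**4. Equal loss per arm**

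The same set-up with 3 patients lost in each arm (1,200 runs) gives +0.0004 to +0.0074 over correlations 0.32 to 1. The sign reverses.

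**5. Loss after Visit 1**

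With LPCF and 6 of 60 lost, the shift is -0.0003 to +0.0049.

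**6. No true effect**

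Under the common cutoff with 6 of 60 lost, shifts are -0.0005 to +0.0002. One-sided rejection at 5% is 4.6% to 5.3%, against 5.2% to 5.4% with full data.

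If loss fell on one arm only, this would not hold. In a simpler model (18 equally correlated outcomes, correlation 0.4, 4,000 runs), removing the worst 10% of the test arm alone under no effect gives MW 0.534 and 20% rejection, against 0.501 and 5.8% with no removal. With d = 0.5, removing the worst 10% of the control arm alone gives MW 0.611 and 75% rejection, against 0.639 and 91%.

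**The case against.** The strongest reply is that the harmful case hardly fits this design. Lack of efficacy would have to be declared in the middle of a fixed course, by a blinded investigator, with no efficacy scale scheduled since baseline. After day 100 no treatment is left to stop, and LPCF covers most of the loss. The list may also serve partly as reason codes for the CRF: withdrawn consent appears among the Investigator's reasons, which suits a recording list better than a rule. The retrieval sentence shows an intent to obtain scores. All of this stands and keeps the point minor. It does not remove the gap, because the section is headed as criteria and no sentence asks for the visits.

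Three stronger readings are tempting, and the documents do not support them:

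- *That the plan nowhere separates stopping treatment from leaving the study.* The dated dosing records, the 80% compliance rule and the one-dose ITT rule all allow for patients who received less than the full course and are still analysed. What is missing is only a requirement to attend after withdrawal.
- *That the loss always pulls the estimate toward 0.5 and so cannot produce a false positive.* That holds for blinded selection on one common cutoff. With equal losses per arm the estimate moves slightly up, and loss confined to one arm could bias either way. Blinding makes one-sided loss implausible, but the text does not exclude it.
- *That the figures describe the SAP's result.* SAP section 12 names Kruskal-Wallis with Dunn's test and Bonferroni adjustment. The shifts above are for the protocol's average MW.

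**Conclusion.** The point holds as an optional improvement of low severity. Protocol 6.3.2 and SAP 13.1 permit a withdrawal that, before Visit 1, removes an obtainable and outcome-related score from the primary analysis. After Visit 1 little is lost.

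The figures are conditional, not expected values. They rest on assumed withdrawal rates, selection strengths and between-visit correlations. Ten percent is an upper case, because it equals the protocol's whole allowance for dropouts and other ambiguities. Since investigators are blinded and have no scheduled scores before day 101, the weak end of the common-cutoff range is the more plausible: -0.002 to -0.003, or about 2% of the design effect. The 18% end needs perfect selection on a score not yet measured. Confidence is medium, mainly because the documents give no withdrawal rate.

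**What to change.** In protocol 6.3.2 and SAP 13.1, make lack of efficacy, and the other Investigator reasons apart from withdrawn consent, grounds for stopping treatment only. Add:

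*Every patient who received at least one dose and has not withdrawn consent to follow-up attends Visit 1 and Visit 2 with the full battery, whether or not treatment was stopped.*

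This also covers patients who stop because they perceive too little benefit but still agree to be seen. On the CRF, record the reason for stopping treatment separately from the date and reason for ending follow-up. Dosing dates are already recorded under protocol 11.2.

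The modified ITT definition needs no change: a dosed patient who stops early and attends Visit 1 then qualifies. The decision to stop treatment stays with the Investigator. The cost is a wording change in two sections, one extra CRF field, and a few more completed visits that are already scheduled for every patient.

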6.4. Randomisation, Blinding and Unblinding

This study will be performed under double-blind conditions to keep investigators, other study personnel and patients blinded to treatment allocation. Cerebrolysin is an amber-colored solution; therefore, colored infusion lines will be used for drug administration.

A set of envelopes for each patient enrolled should be distributed to the study nurse preparing the ready-to-use-infusion solution. These nurses are only responsible for the preparation and administration of infusion solutions, and they should not be involved in any further study-related procedures. This person should not be allowed to disclose any information about treatment allocation. A treatment envelope should not be opened until the patient's first ready-to-use-infusion has been prepared.

Sham stimulation will be performed with a sham-coil (MCF-P-B 65, Magventure) which has a mechanical outline and sound level identical to MCF-B65, and also provides the same level of cutaneous discofort and muscle twiching as real stimulation. The rTMS (both sham and real) administration will be provided by two rTMS technicians which will not be involved in any further study-related procedures and will not be allowed to disclose any information about treatment procedure.

Patients meeting in- and exclusion criteria will obtain a random number corresponding to the random list generated in advance by a biometrician selected by the sponsor. Based on the random list sealed, opaque randomization/emergency envelops will be provided as follows:

Date: 040418

- To the study centre to break blinding if reasonable suspicion of harm to the patients exists
- To the person assigned to prepare the read-to-use-infusion
- To the person assigned to administrate the rTMS protocol.
 - •
 - To the study coordinator

On opening, the randomization/emergency envelopes are dated (date, hour) and signed by the person who has opened the envelope. The Investigator should promptly document and explain to the Sponsor any premature unblinding of the Investigational Product(s). The whole study will be unblinded after closure of the database and determination of the analysis populations.

7. INVESTIGATIONAL PRODUCTS

The Investigational Products will be made available by the sponsor (FSNN)

7.1. Name and Description of the Investigational Products

Cerebrolysin Solution for Injection

Repetitive Transcranial Magnetic Stimulation (rTMS)

7.1.1. Dosage, Formulations and administration

Cerebrolysin Solution for Injection

IV Cerebrolysin (CRB), 30 ml diluted in 0.9% saline solution up to 250 ml, daily during 10 consecutive working days with 3 treatment cycles during study days 32-40, 61-70 and 91-100).

Repetitive Transcranial Magnetic Stimulation (rTMS)

The rTMS treatment will be performed daily during 10 consecutive working days with 3 treatment cycles during study days 32-40, 61-70 and 91-100).

The medical device MagPro X100 (MagVenture, Denmark) will be used for repetitive stimulation with a figure-8 coil (MCF-B65). The coil will be hold tangential to the scalp with the handle pointing upwards. For localizing the left dorsolateral prefrontal cortex (DLPFC) stimulation, we will use the 10-20 EEG system by placing the coil at F3. The stimulation parameters for DLPFC will be set up at 10 Hz and 1,200 stimuli/day, with an intensity of 120% of resting motor threshold. The resting motor threshold is determined at the beginning of the first treatment session and is defined as the minimal intensity at which at least five of 10 motor evoked potentials are 50 μ V in amplitude in the pollicis abductor brevis. For detailed information (SmPCs) on these products please refer to Appendix 1.

7.2. Packaging and Labelling

The investigational product and the reference product will be packaged and labelled for use in clinical trial according to GMP Annex 13 and local legislation.

7.3. Storage

CRB should be kept and stored under 25 degrees Celsius, in its original package.

All supplies must be kept in a locked place, inaccessible to unauthorised persons until they are delivered to the individual patient.

7.4. Investigational Product Accountability and Destruction

The amount of used medication will be recorded in the CRF. All unused medication will be counted and documented and unused investigational products will be destroyed upon completion of accountability.

Date: 040418

8. CONCOMITANT THERAPY

Not allowed concomitant medication: monoamine oxidase inhibitors, antipsychotic drugs or nootropic molecules. All concomittant medications and therapies will be recorded in the CRF.

9. DEFINITION OF THE PRIMARY AND SECONDARY VARIABLES

9.1. Primary Variables

Stroop Color-Word Test

The Stroop Color-Word Test is based on the observation that individuals can read words much faster than they can identify and name colors. The cognitive dimension tapped by the Stroop is associated with cognitive flexibility, resistance to interference from outside stimuli, creativity, and psychopathology – all of which influence the individual's ability to cope with cognitive stress and process complex input. Whether the test is used as a screener or as part of a general battery, its quick and easy administration, validity, and reliability make it an especially attractive instrument. Furthermore, it is not culturally biased (Cohen, 2002). Thus, this unique test is an ideal way to screen for neuropsychological deficits.

MoCA

Montreal Cognitive Assessment (MoCA) was designed as a rapid screening instrument for mild cognitive dysfunction. It assesses different cognitive domains: attention and concentration, executive functions, memory, language, visuoconstructional skills, conceptual thinking, calculations, and orientation. Time to administer the MoCA is approximately 10 minutes. The total possible score is 30 points; a score of 26 or above is considered normal.

Processing Speed Index, Wechsler Adult Intelligence Scale, Third Edition

The Processing Speed Index (PSI) assesses skills such as focusing attention and quick scanning as well as discriminating between and sequentially ordering visual information. It requires persistence and planning ability, but it is sensitive to motivation, difficulty working under time pressure, and motor coordination as well. It is also related to reading, mathematical, and memory

skills. Cultural factors seem to have little impact on processing speed. Processing Speed (PS) refers to the speed at which cognitive processes can be performed.

Digit Span, Wechsler Adult Intelligence Scale, Third Edition

The Digit Span task exercises a patient's verbal working memory. Attention and comprehension also contribute to performance. The digit span task is a common component of many IQ tests, including the widely used WAIS (Wechsler Adult Intelligence Scales). Performance on the digit span task is also closely linked to language learning abilities. The procedures for this assessment of working memory are considered standard. A list of numbers is read out loud at a rate of one number per second, and the participant is then asked to recall the numbers in order. The first list consists of three numbers and increases until the person begins to make errors. Lists with recognizable patterns (e.g., 1, 3, 5, 7, and 9) should be avoided, as people may remember these numbers more easily. At the end of each sequence, the participant is asked to the recall items in order. The average adult can remember a sequence of seven numbers, plus or minus two. This test can be distributed both backwards and forwards. Scores are thought to correlate with age and not intelligence.

Trial Making Test

The Trail Making Test is a neuropsychological test of visual attention and task switching. It consists of two parts in which the subject is instructed to connect a set of 25 dots as quickly as possible while still maintaining accuracy. The test can provide information about visual search speed, scanning, speed of processing, mental flexibility, as well as executive functioning.

The Hamilton Anxiety Rating Scale

The Hamilton Anxiety Rating Scale (HAM-A) is a psychological questionnaire used by clinicians to rate the severity of a patient's anxiety. The scale consists of 14 items designed to assess the severity of a patient's anxiety. Each of the 14 items contains a number of symptoms, and each group of symptoms is rated on a scale of zero to four, with four being the most severe. All of these scores are used to compute an overarching score that indicates a person's anxiety severity.

The evaluator is instructed to assess the extent to which the patient displays the given criterion. Each item is scored independently based on a five-point, ratio scale. A rating of 0 indicates that the feeling is not present in the patient. A rating of 1 indicates mild prevalence of the feeling in the patient. A rating of 2 indicates moderate prevalence of the feeling in the patient. A rating of 3 indicates severe prevalence of the feeling in the patient. A rating of 4 indicates a very severe prevalence of the feeling

in the patient. To implement the Hamilton Anxiety Rating Scale, the acting clinician proceeds through the fourteen items, evaluating each criterion independently in form of the five-point scale described above. Upon the completion of the evaluation, the clinician compiles a total, composite score based upon the summation of each of the 14 individually rated items. This calculation will yield a comprehensive score in the range of 0 to 56. It has been predetermined that the results of the evaluation can be interpreted as follows. A score of 17 or less indicates mild anxiety severity. A score from 18 to 24 indicates mild to moderate anxiety severity. Lastly, a score of 25 to 30 indicates a moderate to severe anxiety severity.

Hamilton Rating Scale for Depression

Hamilton Rating Scale for Depression (HAM-D, is a multiple item questionnaire used to provide an indication of depression, and as a guide to evaluate recovery. The questionnaire is designed for adults and is used to rate the severity of their depression by probing mood, feelings of guilt, suicide ideation, insomnia, agitation or retardation, anxiety, weight loss, and somatic symptoms.

One Touch Stockings of Cambridge

One Touch Stockings of Cambridge is a test of executive function, based upon the Tower of Hanoi test. It assesses both the spatial planning and the working memory subdomains.

Administration time: 10 minutes. Task format: The participant is shown two displays containing three coloured balls. The displays are presented in such a way that they can be easily perceived as stacks of coloured balls held in stockings or socks suspended from a beam. This arrangement makes the 3-D concepts involved apparent to the participant and fits with the verbal instructions. There is a row of numbered boxes along the bottom of the screen. The test administrator first demonstrates to the participant how to move the balls in the lower display to copy the pattern in the upper display and completes one demonstration problem, where the solution requires one move. The participant must then complete three further problems, one each requiring two moves, three moves and four moves. Next the participant is shown further problems and must work out in their head how many moves the solutions require and then select the appropriate box at the bottom of the screen to indicate their response.

Multitasking Test

The Multitasking Test is a test of the participant's ability to manage conflicting information provided by the direction of an arrow and its location on the screen and to ignore task-irrelevant information.

Administration time: 8 minutes

Task format: The test displays an arrow which can appear on either side of the screen (right or left) and can point in either direction (to the right or to the left).

Each trial displays a cue at the top of the screen that indicates to the participant whether they have to select the right or left button according to the "side on which the arrow appeared" or the "direction in which the arrow was pointing". In some sections of the task this rule is consistent across trials (single task) while in others it may change from trial to trial in a randomised order (multitasking). Using both rules in a flexible manner places a higher demand on cognition than using a single rule. Some trials display congruent stimuli (e.g. arrow on the right side pointing to the right) whereas other trials display incongruent stimuli, which require a higher cognitive demand (e.g. arrow on the right side of the screen pointing to the left).

Reaction Time (RTI)

Reaction Time provides assessments of motor and mental response speeds, as well as measures of movement time, reaction time, response accuracy and impulsivity.

Administration time: 3 minutes. Task format: The participant must select and hold a button at the bottom of the screen. Circles are presented above (one for the simple mode, and five for the five-choice mode.) In each case, a yellow dot will appear in one of the circles, and the participant must react as soon as possible, releasing the button at the bottom of the screen, and selecting the circle in which the dot appeared.

